5.3 Evaluation of Objectives

Safety and tolerability will be assessed via the number of patients that experience abnormal seizure activity, show abnormal laboratory values, have increased infection rates, or exhibit an adverse events directly related to treatment with conivaptan. The change in CE volume will be reported as a measure of potential efficacy, and potential impacts on cost of care will be assessed by the length of stay in the ICU and the use of medical interventions to reduce CE volumes. Patient outcomes will be assessed using the mRS at discharge. Due to the small number of patients in this trial and absence of a control group, all evaluation will be descriptive only.

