Subaim 2: Determine the efficiency of obtaining all the study required data and information.

Aim 2: Estimate trends in the safety, tolerability, and efficacy of frequent and early conivaptan use (started within the first 48 hours from ICH symptom onset).

Subaim 1: Estimate if frequent and early use of conivaptan is safe and well-tolerated. [Based on previous work demonstrating conivaptan safety in other models, the working hypothesis is that early and frequent use will be well-tolerated, with few, if any, adverse events.]

Subaim 2: Evaluate the amount of adjunct osmotic therapy (i.e., mannitol, hypertonic saline) given throughout study period.

Subaim 3: Evaluate whether conivaptan reduces the extent of cerebral edema. [The working hypothesis is that early conivaptan use will reduce the presence of AQP4 and limit the development, and thus consequences, of CE.]

3. Background

Intracerebral hemorrhage (ICH) represents ~10-15% of all strokes in the United States (U.S.), numbering 50-70,000 cases per year, twice as common as subarachnoid hemorrhage (SAH), the 30 day mortality is ~40%, and greatest among the poor, elderly, black and Asian (Adams, 2005; Thomas et al., 1996). Only 20% of ICH patients are independent at 6 months. Only admission to a neuro-ICU, and the use of a CT scanner, have been shown to improve outcome from ICH (Thomas et al., 1996; Dinger & Edwards, 2001). With respect to cost, ICH represents 34% of years of potential life lost to stroke (Thomas et al., 1996). Per case, the cost is ~\$124,000, and the total lifetime cost for annual US cases >\$4B (Thomas et al., 1996).

Complicating ICH is the development of cerebral edema (CE). Worsening CE has been implicated in delayed neurological deterioration, and worse outcome, through the elevation of intracerebral pressure (ICP) (Mayer & Sacco, 1994). Elevations in ICP reduce the ability of blood to reach the

brain, exacerbating the injury and producing ischemia. The formation of peri-hematoma edema contributes to an increased volume of ~75% (Gebel et al., 2002). Animal models of ICH demonstrate a large peri-hematoma area that undergoes neuronal death characterized by increased water content and inflammation (Theix & Tsirka, 2007). Reduction of this edema may reduce the degree of neuronal death, decreasing hospital length-of-stay (LOS), and improving short-term outcome (Volbers et al., 2016).

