 5. Development of central pontine demyelination, expansion of initial ICH, new ICH or stroke.

- **Cardiac tolerability:**
 1. Troponin values.
 2. Development of new arrhythmia during ICU stay.

- **Pulmonary tolerability:**
 1. Development of pulmonary edema as determined by chest X-ray.
 2. Average PO₂, FiO₂, A-a gradient.

- **Renal tolerability:**
 1. Change in renal function/urine output. RIFLE criteria will be used to assess for development of renal dysfunction (Appendix 1).
 2. Need for renal replacement therapy (RRT).

- **Infectious tolerability:**
 1. Compare rates of BSI, VAP/HAP, UTI, and sepsis.

- In-hospital mortality stratified by APACHE II, GCS, and ICH Score.

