8.1 Data Reviewed

- Demographics: Age, race, gender, and risk factors (hypertension, diabetes, illicit drug use, coronary artery disease, stroke, alcohol use).
- Clinical Grading Scores:
 - Outcome: mRS (Appendix 2) at baseline and discharge (if available). This can be performed by study team or as part of normal clinical practice.
 - ICH score at baseline (Appendix 5).
 - GCS score at baseline, 24 hrs from enrollment, 72 hrs from enrollment 7 day and discharge (if available) (Appendix 4).
 - APACHE II at baseline (Appendix 3).
- Duration of Neruo-ICU and hospital stay.
- Need for any of the following:
 - EVD/Bolt.
 - Hemi-craniectomy.
 - Central venous line/PICC/Arterial line.
 - RRT.
- Concomitant osmotherapy:
 - Hypertonic saline. The total mEq delivered and form of delivery (i.e. NS vs. 3% NaCl solution vs 23.4% NaCl solution.)
 - Mannitol. Number of doses and total grams received.
- Concomitant medications
- Imaging evaluation: CT scans will be dichotomized and ICH volume and CE volume will be compared over time. The individual summed and averaged volumes, net ICH volume and edema volumes will be compared. A board certified/eligible radiologist will calculate serially

the hemorrhage volume on CT during the study period. ICH volume will be serially assessed both by the $(Ax \times B \times C)/2$ method and by volumetric calculations using volumetric software. Serial assessments of edema will occur by measurements of the length and width of regional edema in the CT slice demonstrating the greatest amount of edema. Volumetric calculations using volumetric software will also be employed to evaluate for CE volume. Further, the same measurements one slice above and below will be performed to allow for a volumetric comparison. Completed CT scan measurements and calculations will be e-mailed to the research coordinator for data entry. In addition to the planned imaging and chemistry panels, any other imaging or basic laboratory work, deemed medically necessary for patient care outside the study, will be evaluated in the final analysis.

Clinical data collected from time of ICU admission to day 7:

- Vital signs (BP, HR, Temp)
- Daily weights and admission height
- ICP/ CPP values- when available/when a monitor is being used
- CVP values- when available
- Volumes for intake and output.
- Na⁺ values
- Cl⁻ values
- Cr values
- BUN values
- PO₂ values- when available
- PCO₂ values-when available
- A-a gradient- when available

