8.3 Data Sharing

- 1) The results obtained from this study will be prepared within a manuscript for submission to a peer-reviewed journal.
- 2) The results will also be used as preliminary data for future studies, including a rigorous, controlled study of the efficacy and safety of conivaptan compared to traditional treatments/a phase II dosing study.

9. Statistical Analysis

Descriptive statistics will be used to summarize the baseline characteristics and the outcomes, such as adverse events and the hospital length of stay. In addition, Mixed model with unequally spaced repeated measures will be performed to evaluate the change of the variables with unequally spaced repeated measures, such as edema content, ICH score, GCS score, and APACHE II score, where unequally spaced repeated edema content measurements for 7 patients will be plotted; while Mixed model with equally spaced repeated measures will be performed to analyze the change of the variables with equally spaced repeated measures, such Mg and PO₄.

10. Study Oversight

The PI and the research team will be responsible for all safety assessments. Safety will be assessed for all patients enrolled in an ongoing fashion based on the incidence of AEs, SAEs, and treatment discontinuations due to AE. If any significant safety issues arise, a decision to modify or terminate the trial will be made. If requested, the study will be made available for monitoring, auditing, IRB review, and regulatory inspection by providing direct access to study related source data to oversight bodies like FDA.

11. IRB Review/Ethics/Informed Consent

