All observations and assessments will be conducted as displayed in Table 1 of the Protocol. Patients will have CT scans at baseline and ~24, 72, and 168 hours (7 days) from enrollment to check for bleeding, lasting edema, or rebound edema. An 8 hour variance is permitted. It is preferable that the CT scans be done at 3mm increments as this is helpful for volume analysis, but 5mm is acceptable. Further imaging is left to the discretion of the treating/primary service physician. Electrolytes (standard-of-care, basic metabolic panel) for all subjects/patients will be measured every 12 hours for the first 72 hours of the study, and then daily after 72 hours. This is considered a regular schedule based on clinical need. However, during the ~48 hour period when the subjects are receiving conivaptan, a comprehensive metabolic panel, Mg, and PO₄ will be drawn and analyzed 6 hours after each conivaptan dose. These labs may be done sooner based on the patient's progress/need and/or the attending physician's direction. Neurological exams (e.g., EEGs), vital signs, and urine output measurements will be conducted as per Neuro-ICU protocol. The need for ancillary monitoring tools (i.e. EVDs, bolts, microdialysis, EEG, near-infrared spectroscopy) will be at the discretion of the treating physicians. Subjects will return for a 3 month follow-up assessment to assess neurological function and a final CT scan.

Study Duration: Each subject is expected to participate in the study for 7 days (including medication administration and wash-out) and the 3-month follow up.

Inclusion Criteria

- Age ≥ 18 years old and < 80 years.
- Diagnosis of primary ICH ≥ 20 cc in volume.
- Enrollment within 48 hours from initial symptoms.
- Signed informed consent from the patient or obtained via their legally authorized representative (if the patient is not able to sign the informed consent themselves). The patient's decisional capacity to either provide or refuse consent will be determined using the Glasgow Coma Scale (GCS), which is being assessed at baseline and at 24 hours (+/- 6hrs) after enrollment. A potential study participant with a GCS > 14 will be asked to provide their own initial study consent. A GCS ≤ 14 would indicate the need to pursue consent via legally authorized representative. Patient and/or LAR must be English speaking.

Exclusion Criteria

- Current need for renal replacement therapy (RRT).
- GFR of <30 mL/minute at time of admission.

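### SAP 5.3 leaves the serial GCS out of the safety assessment, so a neurological decline attributed to the hemorrhage can be absent from the safety count

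*SAP*

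**What the plan says.** SAP 5.3 sets out how the primary objective is judged: "Safety and tolerability will be assessed via the number of patients that experience abnormal seizure activity, show abnormal laboratory values, have increased infection rates". The fourth and last item is patients who "exhibit an adverse events directly related to treatment with conivaptan". SAP 5.4 gives the relatedness judgment to the principal investigator.

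Protocol 8.1 lists the "GCS score at baseline, 24 hrs from enrollment, 72 hrs from enrollment 7 day and discharge (if available". Table 1, which SAP 4 adopts, marks the same times and adds follow-up, where values are recorded if available.

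Protocol 9 names GCS among the variables whose change is to be evaluated by a repeated-measures mixed model: "such as edema content, ICH score, GCS score, and APACHE II score". SAP 5.2 instead makes all analysis descriptive, and its list of analyses does not name GCS. The SAP mentions GCS only in the inclusion criteria, for consent: "The patient's decisional capacity to either provide or refuse consent will be determined using the Glasgow Coma Scale (GCS".

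In Protocol 6.9, GCS enters the safety parameters only as a stratifier: "In-hospital mortality stratified by APACHE II, GCS, and ICH Score". Protocol 6.10 uses it in the same way for mRS.

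**The concern.** Protocol 3 says of cerebral edema: "Worsening CE has been implicated in delayed neurological deterioration". GCS is the only clinical neurological scale scheduled repeatedly through day 7, yet no item in SAP 5.3 reads it. The item that could pick up a decline without seizure, infection or laboratory abnormality is the adverse-event item, and that is limited to events judged directly related to the drug.

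Every patient here has a hemorrhage, so another explanation for a decline is always at hand. There is no control group against which to check the attribution. One unblinded judgment can therefore decide whether a patient who worsened is in the safety count. What is at stake is whether the primary safety result of a seven-patient study shows such a patient at all.

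**Working it through.** The plan has no powered figure to reproduce. Seven patients were chosen from cited studies, time and budget (Protocol 6.4), and both documents say that the study is not powered. The check is therefore a trace of where GCS is collected and used, followed by a small calculation for scale.

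**Step 1. Where GCS appears.**

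| Place | Role of GCS |
|---|---|
| Protocol 8.1, Table 1 | Collected at baseline, 24 h, 72 h, day 7, discharge (if available); Table 1 adds follow-up (if available) |
| Protocol 6.9, 6.10 | Stratifies in-hospital mortality and mRS |
| Protocol 9 | Change over time by mixed model |
| SAP 4, inclusion criteria | Capacity to consent |
| SAP 5.2 list, 5.3, 5.4 | Not named |

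Five scheduled times in seven patients give at most 7 × 5 = 35 values, of which 7 × 4 = 28 are after baseline. These are maxima, because the discharge score is conditional. In Table 1 the doses fall at 0, 12, 24 and 36 h from enrollment. Only the 24 h score lies between the first and last planned doses, and it coincides with the third. The 72 h and day 7 scores follow dosing.

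**Step 2. One patient taken through SAP 5.3.** Suppose GCS falls at 24 h or 72 h, with no seizure, infection or abnormal laboratory value, and the investigator attributes the fall to the hemorrhage.

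- Seizure item: not met.
- Laboratory item: not met.
- Infection item: not met.
- Related adverse event: not met, because of the attribution.

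The patient is outside the 5.3 count. The same can happen with other neurologic events that Protocol 6.9 lists as safety parameters and SAP 5.3 does not name: "Development of central pontine demyelination, expansion of initial ICH, new ICH or stroke".

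**Step 3. Where the same patient can still appear.** SAP 5.4 requires all adverse events to be collected, related or not. SAP 5.2 plans a frequency of complications considered relevant, a term it does not define. Discharge mRS (SAP 5.3) and the 3-month neurological assessment (SAP 3 and 4) may reflect a lasting decline. None of these places the patient in the 5.3 safety count, and neither late measure can date a decline or show one that has recovered.

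**Step 4. Size.** One patient of seven is 1/7 = 14.3 percentage points. Exact (Clopper-Pearson) 95% limits, which the SAP does not plan and which are given only for scale:

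- 0/7: lower limit 0; upper limit 1 − 0.025^(1/7) = 0.410.
- 1/7: lower limit 1 − 0.975^(1/7) = 0.004; upper limit is the p that solves (1 − p)^7 + 7p(1 − p)^6 = 0.025, which is 0.579.

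One omitted patient thus separates 0/7 (0%, 0 to 41.0%) from 1/7 (14.3%, 0.4 to 57.9%), if no other patient is counted.

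**The case against.** The strongest reply is that the plan already captures deterioration. A material GCS fall fits the SAP 5.4 definition of an adverse event, which does not depend on relatedness. SAP 5.2 reports complications, and SAP 5.3 reports interventions to reduce edema, which a treated decline could trigger. Protocol 10 assesses safety on the incidence of adverse and serious adverse events with no relatedness filter, and Protocol 9 still plans a GCS model. With sedation permitted, seven patients and no control, a GCS count could not separate drug harm from the course of the disease.

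Much of this stands, and it rules out several stronger readings that a reader might infer:

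- *That a GCS fall would change no planned summary.* SAP 5.2 and 5.4 contradict this.
- *That the GCS values have no planned use.* This is true of the SAP's analyses but not of the whole plan, because of Protocol 9. The SAP does not say that it replaces that section.
- *That discharge mRS is the only functional measure.* SAP 3 and 4 provide a 3-month outcome and neurological assessment.
- *That the chance of any deterioration measures the defect.* The documents give no deterioration rate. Assuming 20 to 40%, the chance that at least one of seven patients deteriorates is 1 − 0.8^7 = 79% to 1 − 0.6^7 = 97%. That is not the chance that a patient is lost from the safety result. Loss also requires an unrelated attribution and no other 5.3 item being met.

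What the reply does not answer is the 5.3 count itself. No GCS change is defined as an adverse event, so recording one depends on judgment, and 5.3 then keeps only related events. The Protocol 9 model is not tied to safety, would not count patients who worsened, and conflicts with the descriptive-only rule.

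**Conclusion.** The point holds as a gap in the primary safety summary; the data collection itself is adequate. Under SAP 5.3 as written, a patient whose GCS falls, whose decline is attributed to the hemorrhage and who meets no other item is recorded elsewhere but can be absent from the safety count. Each such patient is worth 14.3 percentage points. In the simplest case the result reads 0/7 (exact 95% CI 0 to 41.0%) instead of 1/7 (14.3%, 0.4 to 57.9%).

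This rests on two assumptions: that 5.3 is applied as worded, and, for the 0/7 against 1/7 comparison, that no other patient is counted. How often such a patient would arise cannot be estimated from the documents. The change is worth making because it is cheap, uses scheduled data and removes the dependence on attribution. It would not show whether conivaptan caused a decline.

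**What to change.** In SAP 5.3:

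- Add a per-patient listing of GCS at all scheduled times.
- Add a count of patients with a prespecified fall in GCS from the last value before the first dose, regardless of relatedness. The documents give no threshold, so the sponsor should set one before analysis.
- Flag values taken under sedation or intubation, and show deaths separately.
- Tabulate all adverse events and serious adverse events beside those judged related. Events of the kinds that Protocol 6.9 lists and 5.3 omits would then be visible too, where they are recorded as adverse events.

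Reconcile Protocol 9 with the descriptive-only rule in SAP 5.2: either state that the GCS mixed model is withdrawn in favor of the listing and count, or keep it and say what it is for.

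The cost is some SAP wording, a listing of seven rows and a small table. No new assessment and no change in sample size is needed. The downside is that some values under sedation or intubation will not be interpretable, which the flags make plain.

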6.9 Primary Assessments (Safety and Tolerability)

Conivaptan was approved by the FDA in 2005 for the treatment of euvolemic and hypervolemic hyponatremia in a hospitalized setting using doses of 20-40mg/day. In the 11 years it has been on the market, numerous studies using it at doses ranging from 20-80mg/day have been done furthering the data on its effect on hyponatremia (National Monograph, 2006; Ghali et al., 2009; Zeltser et al., 2007; Verbalis et al., 2008; Annane et al., 2009; Human et al., 2012; Marik & Rivera, 2013), as well as studies showing its lowering of ICP in patients with TBI (Dhar & Murphy-Human, 2011; Galton et al., 2011). These benefits should relate to a decrease in CE.

In all these studies, conivaptan was well tolerated and safe, with no drug-related serious adverse events observed. For example, in the Ghali et al (2009) study, no deaths were study related, and the side effects of headache, hypotension, nausea, and constipation occurred most frequently. Based on these observations, we expect only minimal, if any, side effects in our study, since we are using a dose (40mg/day) which is lower than the 80mg/day used in several of the above mentioned studies. And, we feel there are no special concerns in the patient population included in our study (non-traumatic ICH) since conivaptan has already been safely used in TBI ICH patients.

An evaluation of the safety assessment parameters of each of the seven (7) subjects will be done by the PI and Co-I during the patient's care. Should events occur regarding the administration of conivaptan that raise safety concerns, the PI has the authority to withdraw the subject and/or halt the study pending further investigation.

Specific safety assessment parameters will include the following-

- **Neurologic tolerability:**
 1. Seizure frequency (15-20% of patients with ICH have seizures associated; EEGs will be used and measured; all treatments will be the same, using anti-seizure drugs).
 2. Total Na+ mEq received.
 3. ICP variability. In all patients for whom ICP is monitored, the hourly mean and median ICP will be compared. Further, patients will be graphed and the area-under-the-ICP-curve and above 10, 15, and 20 mmHg will be calculated and averaged to provide a more continuous comparison.
 4. ICP response to osmotic therapy. In patients receiving mannitol or 23.4% NaCl boluses, the average ICP reduction in the hour following administration will be compared.

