7.1 Risks and Benefits

7.1.1 Potential risks

Potential risks associated with conivaptan may include hypotension, excessive rise in serum sodium, development of central pontine myelinolysis, increase in seizure frequency, expansion of initial ICH, development of new ICH and/or stroke, development of new cardiac arrhythmia, development of pulmonary edema, change in renal function, and development of an infection.

Potential risks involving blood draws may include temporary discomfort from the needle stick, pain or bruising, lightheadedness, and infection at the site.

Potential risks of CT scans are exposure to radiation from X-rays, dizziness, cold sensation at injection site, worsening of poor kidney function, allergic reaction to injection dye, soreness or swelling at the injection site.

Potential risks will be minimized by blood pressure monitoring, monitoring of total Na⁺ mEq received, EEG monitoring and measurement (15-20% of patients with ICH have seizures, anti-seizure medications will be used), ICH/ICP monitoring, monitoring of troponin levels, chest x-ray and monitoring of pulmonary parameters (such as PO₂, FiO₂, A-a gradient), assessment of renal function by the RIFLE criteria, monitoring for infections.

Training sessions for all clinical study personnel will occur prior to the start of the study to discuss the potential risks that could occur, and the monitoring for and treatments that are in place.

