The study population consists of patients with ICH at risk for developing CE.

a. Primary Objective – Safety and Tolerability

An evaluation of the safety assessment parameters of each of the seven (7) subjects will be done by the PI and Co-I during the patient's care. Should events occur regarding the administration of conivaptan that raise safety concerns, the PI has the authority to withdraw the subject and/or halt the study pending further investigation.

b. Secondary Objectives

Several secondary hypotheses can be tested for data generated by this investigation:

1. Reduction in CE as measured on CT. Goal is a 5-10% reduction in CE over time.
2. Patient outcomes: the modified Rankin Scale (mRS) will be used to assess patient outcomes at hospital discharge. This scale assess functional deficits on a scale from 0 (no deficit) to 6 (death).
3. Cost of care: Several proximal measures will be used to assess cost, including length of stay in the ICU, the need for EVD/bolt or surgical procedures to reduce or manage CE, the need for lines (central venous, arterial, PICC) or tracheostomy/PEGs, and the number of patients that required ventilation.

Study Endpoints

1. Laboratory values: assessment will end at the completion of conivaptan administration (Day 3).
2. Long-term Outcome: Patients will be observed for three months, beginning at enrollment, to determine long-term outcomes of conivaptan treatment.

4. Investigation Plan

This a single-center, open-label prospective study which aims to evaluate the safety and tolerability of conivaptan in patients with ICH that are at risk for developing CE. The study will include 7 patients with a diagnosis of ICH that is ≥ 20 cc in volume, aged between 18 – 80 years. All patients will receive 20mg IV of conivaptan every 12 hours equaling 40mg/day over 2 days (4 doses total), in addition to the standardized ICH management.

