- Participation in another study for ICH or intraventricular hemorrhage.
- ICH related to infection, thrombolysis, subarachnoid hemorrhage, trauma or tumor.
- Presence of HIV or active fungal infection that is known based on information in the EMR.

- Continued use of digoxin or amlodipine (as recommended by the manufacturer due to CYP3A inhibition).
- Active hepatic failure as defined by AST >160 units/L and/or ALT >180 units/L, or total bilirubin levels greater than four times normal levels (>4.8mg/dL).
- Serum Na⁺ ≥ 145 mmol/L (admission labs or any time prior to recruitment/enrollment).
- Unable to receive conivaptan based on contraindications indicated by the manufacturer.
- Pregnant or lactating females.
- Not expected to survive within 48 hours of admission, or a presumed diagnosis of brain death.

5. Statistical Methods

5.1: Study Subjects and Analysis Sets

All enrolled patients will be included in a single analysis set and data will be summarized using frequencies and percentages.

5.2: General Methodology

This study is looking to preliminarily evaluate the safety, tolerability, and efficacy of conivaptan treatment. Unfortunately, it is not powered to provide robust statistical evaluation of safety and tolerability, nor to detect differences in efficacy between subjects. As such, all analysis will be descriptive in nature. Categorical variables will be summarized using counts and percentages. Continuous variables will be summarized using descriptive statistics: number of patients, mean, median, and full range, as appropriate.

Statistical analysis will consist of:

- Descriptive analysis of patient characteristics
- Frequency of relevant complications and medical interventions
- Changes in CE volume

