5.4 Safety Evaluation

Subjects will be monitored throughout their hospital stay. Adverse events (AE) will be assessed in terms of their seriousness, duration, intensity, and relationship to the study drug. All

anticipated and unanticipated AE will be collected. Subjects will be able to contact the investigator at any time during the study. The outcome of each event, including any interventions used, will be observed and documented.

a. Adverse Event Definitions and Reporting Requirements

An AE is any complaint or untoward medical occurrence that is an unintended disease or injury or untoward clinical sign (including abnormal laboratory findings) in a subject, whether or not it is related to the investigational drug.

A Serious Adverse Event (SAE) is an untoward medical occurrence in a subject that may or may not be related to the investigational drug, but that meets the criteria of “serious” by resulting in one of the following outcomes:

- Death
- Requires initial or prolonged inpatient hospitalization
- Is life-threatening (that is, immediate risk of dying).
- Is a persistent or significant disability/incapacity.
- Other significant medical hazard.

All adverse events will be collected and documented throughout the study. The PI will assess each AE to determine severity, relatedness to the study drug, and if it was anticipated or unanticipated.

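### SAP 5.3 counts adverse events toward the primary safety objective only when directly related to conivaptan, a condition that Protocol 6.9 and 10 do not set

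*SAP*

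**What the plan says.** SAP 5.3 is the one place in the SAP that says how the primary objective is to be evaluated. It counts patients with abnormal seizure activity, and patients who "show abnormal laboratory values, have increased infection rates, or exhibit an adverse events directly related to treatment with conivaptan". The first three items carry no attribution condition. The fourth does.

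Protocol 6.9, which sets out the primary assessments, introduces its list with "Specific safety assessment parameters will include the following". Among the items is "Development of central pontine demyelination, expansion of initial ICH, new ICH or stroke". The cardiac and pulmonary items include new arrhythmia during the ICU stay and pulmonary edema on chest X-ray. Each is recorded when it develops, with no causality test.

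Protocol 7.1.1 gives the potential risks of conivaptan as including "development of central pontine myelinolysis, increase in seizure frequency, expansion of initial ICH, development of new ICH and/or stroke, development of new cardiac arrhythmia", and goes on to pulmonary edema. Protocol 10 bases ongoing safety assessment on how often AEs, SAEs and AE-driven discontinuations occur, whatever their cause.

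The SAP has other text on these events. Section 3, Primary Objective, states: "An evaluation of the safety assessment parameters of each of the seven (7) subjects will be done by the PI and Co-I". Section 5.2 plans "Frequency of relevant complications and medical interventions". Section 5.4 states: "Adverse events (AE) will be assessed in terms of their seriousness, duration, intensity, and relationship to the study drug".

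**The concern.** In a single-arm study of seven patients, the descriptive count is the whole of the primary result, so the rule for what enters it matters. The protocol names five kinds of event as possible harms of the drug, and the hemorrhage itself can plausibly explain most of them. With no control group, the PI can reasonably judge such an event not directly related. Followed as written, SAP 5.3 would then leave it out of the safety count. The event would remain in the AE record, but the summary supporting a statement that the drug was safe and well tolerated need not show it.

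The working hypothesis in Protocol Section 2 (Aim 2, Subaim 1) is that there will be few adverse events, not few directly related ones. A count restricted by attribution does not address it as worded. The results are also meant as preliminary data for a later controlled study (Protocol 8.3), so an omission could carry forward into its design.

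**Working it through.** The plan gives no figure to reproduce. It states no power, alpha or event rate, and it says the study is not powered. The check is a comparison of texts, followed by a short illustration.

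**Step 1. Route of each Protocol 6.9 event type into the SAP.**

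| Protocol 6.9 event | SAP 5.3 | Other possible SAP route |
|---|---|---|
| Seizure | named, no attribution needed | – |
| Renal change | arguably via abnormal laboratory values | – |
| Infection | named, as increased rates | – |
| Renal replacement therapy | not named | arguably a medical intervention (5.2) |
| In-hospital death | not named as a safety count | mRS 6, under patient outcomes |
| Central pontine demyelination | only if a directly related AE | general summaries in 5.1 and 5.2; complications line in 5.2 |
| ICH expansion | as above | as above |
| New ICH or stroke | as above | as above |
| New arrhythmia | as above | as above |
| Pulmonary edema | as above | as above |

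This makes 10 event types. Three are credited to 5.3, which leaves 10 − 3 = 7 unnamed. Setting aside death and renal replacement therapy leaves 7 − 2 = 5. Splitting new ICH from stroke, or not crediting renal change to laboratory values, adds one each, so the range is 5 to 7. All five are potential risks in Protocol 7.1.1.

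**Step 2. Meaning of the condition.** Protocol 7.2 has two categories, related and unrelated. Related requires at least a reasonable possibility that study procedures caused or contributed to the event. SAP 5.3 adds *directly*, which neither document defines and which reads as narrower than *contributed*. The scales also differ: Protocol 7.2 rates relation to study procedures, SAP 5.4 to the study drug.

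**Step 3. Consistency within SAP 5.3.** Seizures count without attribution, although Protocol 6.9 puts their frequency in ICH at 15–20%. A background rate from the disease is therefore not the SAP's reason for filtering the other events.

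**Step 4. ICH expansion.** This event needs no attribution to be measured. Protocol 8.1 says of the serial CT scans that "ICH volume and CE volume will be compared over time", and SAP Section 4 says the scans check for bleeding. SAP 5.2 and 5.3 nevertheless list only the change in CE volume.

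**Step 5. Illustration with n = 7.** One patient is 1/7 = 14.3%. Suppose one patient has ICH expansion. A per-event table following Protocol 6.9 shows 1/7 (exact 95% CI 0.4–57.9%). If the event is judged not directly related, it adds nothing to the related-AE item of SAP 5.3; 0/7 has an exact 95% CI of 0–41.0%.

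For an assumed per-patient risk p and an assumed share q judged directly related, the chance that at least one event is counted is 1 − (1 − pq)^7. With p = 0.20:

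- q = 1: 1 − 0.80^7 = 79%
- q = 0.5: 1 − 0.90^7 = 52%
- q = 0.25: 1 − 0.95^7 = 30%

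With q = 0.25 and p from 0.10 to 0.40, the chance runs from 16% to 52%, against 52% to 97% when every event counts. Both p and q are assumptions; the documents give neither.

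**The case against.** The best case for the plan is that SAP 5.3 is a short summary and 5.4 the fuller evaluation. SAP 5.3 does not say that other AEs are excluded. SAP 5.4 follows directly under Statistical Methods, defines AEs and SAEs whatever their cause, and treats relationship as one of four attributes. SAP 5.1 and 5.2 promise counts and percentages for the data in general. SAP Section 4 adopts the protocol's assessment table, which includes an adverse event log. Protocol 9 plans descriptive summaries of adverse events, and nothing in the SAP revokes that. The Protocol 7.2 threshold for related is also low enough that a listed drug risk could readily meet it.

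Much of this stands. A reader might infer that the five events are lost, or that the attribution filter is their only way into any report. The documents support neither reading: the events are collected, and several general routes could carry them. A reader might also take the change from 1/7 to 0/7 as the bias in the SAP 5.3 result. It is not. SAP 5.3 produces no separate count for ICH expansion and does not say whether its items form a composite. If they do, a patient with an abnormal laboratory value is counted anyway. The SAP plans no confidence intervals either.

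What the objection does not supply is a commitment. SAP 5.4 promises collection, documentation and assessment, not a table. The complications line in 5.2 leaves *relevant* undefined and open to decision after the data are seen. SAP Section 3 describes review during care. Protocol 10 concerns ongoing oversight, but its unfiltered basis still differs from SAP 5.3. If Protocol 9 means all AEs, it too has to be reconciled with 5.3.

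**Conclusion.** The concern holds as a conflict between SAP 5.3 and Protocol 6.9 and 10 over what counts toward the primary objective, made worse by an undefined term. Five protocol-named primary safety events (5 to 7 depending on how items are split) enter the SAP 5.3 evaluation only through PI attribution in an open-label, uncontrolled study.

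The consequence is possible under-counting in the reported primary safety result. Its size cannot be estimated, because the documents give neither event rates nor the share likely to be judged directly related. All analysis is descriptive, so no test, power or formal decision rule is affected. The conclusion assumes that SAP 5.3 is applied as written. It does not assume that the PI would attribute events wrongly, and nothing in the documents suggests that.

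**What to change.** In SAP 5.3, remove direct relatedness as a condition for counting, and add one safety table that shows, regardless of attribution:

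- n/N for each Protocol 6.9 event, with ICH expansion taken from the serial CT ICH volumes under a definition stated in advance;
- all AEs, all SAEs and discontinuations due to AE;
- relatedness as a secondary column on one scale mapped to Protocol 7.2, settling whether it refers to study procedures or to the study drug.

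Define the relevant complications in SAP 5.2 as this same list. As a separate wording repair in the same sentence, replace increased infection rates, which has no comparator and is not a patient-level event, with the number of patients with at least one BSI, VAP/HAP, UTI or sepsis.

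The cost is SAP wording and one table from data already planned for collection. The downside is that reported event rates will look less favourable and many events will reflect the hemorrhage itself; the text with the table should say so.
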